5.3.4 ACTIVE GROUP: ORAL IMMUNOTHERAPY

Subjects randomized to the active intervention arm will continue to undergo an OPEN (unblinded) food challenge at the same visit, to determine the starting dose of boiled peanut. This is because some children may exhibit a degree of *de novo* tolerance to boiled peanut, and thus demonstration of tolerance allows for individualization of the updosing protocol. The open challenge will utilize the following protocol:

Protocol 2: Open OFC to boiled PN	Boiled peanuts (If dose tolerated, commence		
TIME POINT (mins)	No. peanuts Peanut protein (mg)*		updosing at STEP:	
(Already given in 5.3.1)	¼ boiled peanut	30	pre-A	
0	¾ boiled peanut	100	1	
30	2 boiled peanuts	260	1	
60	4 boiled peanuts	520	1	
90	8 boiled peanuts	1040	5	
Cumulative dose 15 boiled peanuts 1950				
2 hours observation period following last dose to monitor for signs of reaction				

^{*}Boiled peanuts contain approximately half the amount of protein as roasted peanuts.

The criteria listed in Section 5.2.2 will be used to determine outcome of this food challenge.

Children will receive daily doses of peanut at home, initially using boiled peanut. The updosing regime is shown in Table 1. Children who tolerate at least 1 boiled peanut will commence updosing at ½ boiled peanut, unless they have passed the challenge in its entirety (i.e. tolerates 15 boiled peanuts) in which case they will commence at STEP 5. Those who tolerate ¼ boiled peanut only will commence updosing at the pre-A step (Table 1).

Children in the ACTIVE group (and their parents) will undergo quality-of-life assessments at 0, 3, 6 and 12 and 24 months (see section 5.7.1).

Prior to discharge home, each family will be provided with:

- A symptom advice sheet (including advice on avoiding intense physical exercise up to 2 hours after the dose intake).
- A food allergy management plan (Figure 6), including an emergency medicine kit containing non-sedating oral
 antihistamine and two adrenaline auto-injectors. Where the child has a history of asthma or prior respiratory
 symptoms to a food allergen, the kit will also include a salbutamol inhaler and spacer device. Families and
 participants will be instructed in the prompt recognition and treatment of allergic reactions, including
 adrenaline auto-injectors.
- **Contact information** for the team, which will includes a dedicated mobile phone number with 24/7 access to a senior member of the medical team for urgent queries, and an email address which will be checked daily by the research team from Monday to Friday for non-urgent queries.
- **Dietary advice on peanut avoidance**. Participants receiving OIT will not be allowed to ingest peanut for the whole study duration (52 weeks) excluding the OIT doses.
- A home diary and instruction sheet, which will specify to parents what dose to give their child, and on to which they will log all doses taken at home and any resulting adverse events. Subjects will be asked to record any symptoms, duration, timing in relation to OIT dose and any exacerbating factors (e.g. exercise, excessive tiredness, viral illness). In the event of any symptoms, the family needs to contact the research team for advice. Participants will also be offered an opportunity to 'opt-in' to using an electronic 'mobile app' diary in parallel to the paper-based diary, the aim being to facilitate reporting by study participants and validate this approach for future OIT studies.

5.3.4.1 UPDOSING

At each step (i.e. all dose increases), the dose will first be given under medical supervision on the Research Unit, followed by observation for at least one hour (2 hours if participant has previously experienced a delayed reaction). Prior to a dose increase, the supervising clinician will assess the participant to ensure:

- No significant allergic reactions to doses given in previous 2 weeks.
- No acute exacerbation of asthma in the past week.
- No concurrent systemic illness.

The dose can be mixed into a carrier (such as low fat (rather than full fat) yoghurt, for example) if desired. Children will be monitored under medical supervision for one hour following dose administration. Following each dose increase, that dose will be given to participants at home daily for a minimum of 2 weeks until the next increase is performed.

STEP	PEANUT Boiling time	No. of peanuts / day	No. weeks at this dose (minimum)	Cumulative No. of weeks (minimum)	Approximate Peanut protein (mg)
pre-A	4 hours	1/8	2	-	15
pre-B	4 hours	1/4	2	-	30
1	4 hours	1/2	2	2	65
2	4 hours	1	2	4	130
3	4 hours	2	2	6	260
4	4 hours	4	2	8	520
5	4 hours	8	2	10	1040
6	2 hours	4*	2	12	520
7	2 hours	8	2	14	1040
8	1 hour	2*	2	16	260
9	1 hour	4	2	18	520
10	1 hour	8	2	20	1040
11	1/2 hour	4*	2	22	520
12	1/2 hour	8	4	26	1040
	Open OFC to	roasted peanut (t	o determine if u	pdosing can be co	onverted to roasted):
		_	=	•	anuts up to Wk 52
	• If tole	erates 300mg dose	e, continue updo	osing as follows:	
13	n/a	½ roasted PN	4	30	125
14	n/a	1 roasted PN	4	34	250
15	n/a	2 roasted PN	4	38	500
16	n/a	4 roasted PN	4	42	1000

Table 1: Updosing protocol for Peanut (PN) OIT using boiled and then roasted peanut.

5.3.4.2 TRANSITION TO ROASTED PEANUT

After STEP 12 (approximately 4-7 months after commencement), the next updosing step involves a transition to roasted peanut. This will involve an OPEN (unblinded) abbreviated food challenge according to the following protocol:

^{*}For initial (in-hospital) updosing at the time points marked, the dose to be administered will be split into 2 doses, given 30 minutes apart: Step 6: 1 + 3 peanuts; Step 8: 1 + 1 peanut; Step 11: 1 + 3 peanuts.

Protocol 3: Open OFC to roasted PN	Roasted peanut OFC	If dose tolerated,			
TIME POINT (mins)	Peanut flour (mg) Peanut protein (mg)		continue at STEP:		
0	20	10	Do not transition to		
30	60	30	roasted PN: continue		
60	200	100	at 8 boiled PN per day		
90	600*	300*	13		
150	2000	1000	13		
180	6000 [#]	3000 [#]	16		
Cumulative dose 4440mg					
2 hours observation period following last dose to monitor for signs of reaction					

^{*}Dose to be given as 1 whole peanut (25% protein) + peanut flour to make a total dose of 300mg peanut protein

The criteria listed in Section 5.2.2 will be used to determine outcome of this food challenge.

Children who tolerate at least 300mg peanut protein (i.e. a cumulative dose of 440mg) will continue updosing at STEP 13 using roasted peanut. Those who tolerate the entire dose (4440mg) will continue at STEP 16. This is equivalent to continuing OIT at a minimum of one half roasted peanut BELOW that tolerated at this open challenge. Children who are unable to tolerate the 300mg dose will continue maintenance at 8 boiled peanuts (boiled for 30mins) until the 1 year assessment.

All subjects will also undergo repeat skin prick testing to commercial crude peanut extract, and quality-of-life assessments as described in section 5.7.1.

5.3.4.3 CHANGES TO THE PROTOCOL DUE TO REACTIONS

In the event of an allergic reaction to a dose of OIT within 2 hours of a dose, either at updosing in hospital or after a dose given at home, the following measures will be taken:

- For a single reaction consisting of wheeze, persistent cough, difficulty breathing, stridor or marked swallowing difficulties, the family must not give further OIT doses without contacting the research team. The previous lower dose will be given the next possible day, ideally under medical observation on the Research Unit.
- For skin symptoms, itchy mouth, rhinoconjunctivitis or mild abdominal symptoms, reassurance to families will be provided and the current dose will be continued, with daily contact with the study team as needed.
- For persistent reactions for 5-7 days (within 2 hours of the OIT dose) consisting of abdominal pain, rhinoconjunctivitis or skin symptoms, the dose will be reduced to the previous dose.
- In the event of other symptoms that prove difficult to the child, the dose can be reduced at investigator's discretion.

Where a dose reduction is required, the subsequent dose increase will be performed at least 2 weeks later at the Research Unit in hospital under supervision.

In the event of omitted doses:

- If a single dose of OIT is missed, the subject can continue with the usual dose.
- If 2 4 days of OIT are missed, give the previous dose until the subject can attend the research unit for the next updosing.
- If more than 4 days are missed, daily doses should stop and the subject must attend the research unit.

In the event of an intercurrent illness, where symptoms occur but are not related temporally to dose administration, families should contact the research team to discuss reducing the dose depending on symptoms type and intensity.

 $^{^{\#}}$ Dose to be given as 4 whole peanuts + peanut flour to make a total dose of 3 gram peanut protein

5.3.4.4 PREPARATION OF BOILED AND ROASTED PEANUT FOR OIT

Families will be provided with blanched raw peanut at hospital visits, for preparation at home. Full instructions will be provided (as part of the **home diary and instruction sheet**). Peanuts (Holt Runner cultivar, supplied by the Peanut Company of Australia Ltd) will be supplied in 125g vacuum-packed batches to families on an as-needed basis, in order to monitor peanut consumption.

Families will be provided with instructions to boil the peanuts at home in batches, as follows:

- Boil 100g quantity of peanuts in a saucepan in ~600ml water for xx hours
- Drain and plunge peanuts into cold water, then drain in colander/sieve
- Lay peanuts in a single layer on a baking tray lined with baking paper
- Place tray in freezer until peanuts are 'snap frozen'
- Transfer peanuts into a plastic container and store in freezer until required.

The boiling time will be progressively reduced as depicted in Table 1 above.

In those children who tolerate roasted peanuts, families will be instructed to use commercial roasted peanuts (KP roasted peanuts) sourced from a UK supermarket. Alternatively, peanut M&Ms may be substituted for roasted peanut, where this is desired by the study participant: four roasted peanuts is equivalent to 6 peanut M&Ms.

5.4 1 YEAR ASSESSMENT

All subjects, in both the active (OIT) and control groups, will be invited to undergo a further DBPCFC to roasted PN at 12 months. Those who tolerate >1.4g of peanut protein at this challenge will be invited back for a further open challenge having stopped all peanut ingestion (including OIT doses) for 4 weeks. The challenges and outcomes are depicted in summary form in Figure 7.

[figure not shown]

Figure 7: Challenges and outcomes, months 12-13

All subjects will also undergo repeat skin prick testing to commercial crude peanut extract, and quality-of-life assessments as described in section 5.7.1.

Imperial College

5.4.1 12 MONTH DBPCFC

The DBPCFC will be performed as per Protocol 1 in Section 5.2.2. The purpose of this challenge is:

- In those who have undergone OIT, to assess for desensitisation to roasted peanut and a resulting change in threshold of clinical reactivity (Primary and Secondary outcome measures).
- In the control group, to determine the rate of natural resolution of peanut allergy and for those continuing into WP2 (where they will undergo OIT), serve as the baseline threshold of clinical reactivity to roasted peanut.

Protocol 1: DBPCFC to roasted PN	Roasted peanut DBPCFC (using defatted flour)		OUTCOME if reacts
TIME POINT (mins)	Peanut flour	Peanut protein	
0	6	3	
30	20	10	OUT.
60	60	30	OIT unsuccessful: withdrawn from study*
90	200	100	withdrawn from study
120	600	300	
150	2000	1000	Continue daily PN at previous maintenance dose
180	6000	3000	STOP peanut for 4 weeks and proceed to open challenge
Cumulative dose	4440mg		If no reaction:
2 hour observation period following last dose		STOP peanut for 4 weeks and proceed to open challenge	

^{*}In the unlikely event that a child reacts to the 300mg dose during challenge but has previously tolerated ≥1 roasted PN, then they can continue daily peanut at the previous tolerated dose for a further 12 months, within this protocol.

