- 5. **WP2:** Those subjects in the control group will be offered OIT using boiled PN during months 12-24. Subjects in the active intervention groups will be offered ongoing maintenance therapy within the study protocol.
- 6. **2 year assessment** and option to determine longer-term tolerance to peanut.

Subjects will be invited to remain in the study for a 3rd year to allow longer-term evaluations to be performed.

The efficacy and impact of OIT on quality of life will be assessed at 6, 12, 24 and 36 months in all subjects (and their parents), using a validated questionnaire.

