4.3. WITHDRAWAL CRITERIA

Subjects will be free to withdraw from the study at any time without affecting their future medical care. Subjects who are withdrawn from active treatment will remain in the study for assessment of outcome relating to QoL measures.

The safety of the child is paramount in this study. Thus, children who experience anaphylaxis to an OIT dose at home, but who do not receive IM adrenaline as per the management plan, will have further updosing suspended until the family undergo retraining on the recognition and management of allergic symptoms.

A participant will be withdrawn from the study under the following circumstances:

- If, in the opinion of the study team, compliance with study procedures is suboptimal such that it compromises the patient's safety.
- If, in the opinion of the study team, further participation would adversely affect the participant's health.
- A child develops an exclusion criteria during the updosing phase of the study e.g. a new medication (which would normally be a contra-indication) is commenced.
- If consent is withdrawn or the subject fails to return for a study visit.
 In the event of a serious adverse reaction to OIT and/or if presenting with anaphylaxis requiring more than one IM adrenaline dose within 2 hours after an OIT dose.

Any subject excluded from further participation will not be replaced.

⁹ Sporik R, Hill DJ, Hosking CS. Specificity of allergen skin testing in predicting positive open food challenges to milk, egg and peanut in children. Clin Exp Allergy 2000; 30:1540–6.; AND Sampson HA. Utility of food-specific IgE concentrations in predicting symptomatic food allergy. J Allergy Clin Immunol 2001;107: 891–6.

¹⁰Papadopoulos NG, Arakawa H, Carlsen KH, et al. International consensus on (ICON) pediatric asthma. Allergy. 2012;67:976-97.

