5.5 WP2: YEAR 2 OF STUDY

Children in the control group will be offered OIT using boiled PN during months 12-24. An identical protocol to WP1 will be used (section 5.3.3).

Children in the active group (who underwent OIT during months 1-12) will be offered ongoing maintenance therapy, as described above in section 5.4.

5.6 2 YEAR ASSESSMENT

Children who were originally assigned to the control group and who have undertaken OIT during months 12-24 will undergo a further DBPCFC to roasted PN at 24 months. The DBPCFC will be performed as in Section 5.2.2. The purpose of this challenge is to assess for the development of sustained unresponsiveness to roasted peanut following OIT, and the resulting change in threshold of clinical reactivity.

All subjects will also undergo repeat skin prick testing to commercial crude peanut extract and boiled peanut slurry, and quality-of-life assessments as described in section 5.7.1.

All children (in both control and active groups), apart from those who passed the tolerance challenge at 13 months, will be offered a further tolerance challenge at 24 months, to be performed as in section 5.4.

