5.7 YEAR 3/4 ASSESSMENTS

All children (in both active and control groups) will be invited to return at the 3 year timepoint for a further set of challenges, to define longer-term tolerance following 2-3 years of active immunotherapy. This is because there is data to suggest that longer duration of OIT is associated with immune memory and more sustained tolerance. These assessments will consist of:

- i. A DBPCFC at the year 3 timepoint (3 years following randomisation) (conducted according to section 5.4.1)
- ii. Open food challenge 4 weeks after stopping OIT (identical to tolerance challenge, section 5.4.2)
- iii. In participants who exhibit sustained unresponsiveness at 4 weeks, a further DBPCFC (conducted according to section 5.4.1) after a further 8 weeks off OIT, to assess for sustained unresponsiveness at 12 weeks.
- iv. In participants who exhibit sustained unresponsiveness at 12 weeks, a further DBPCFC (conducted according to section 5.4.1) after a total of 1 year off OIT, to assess for sustained unresponsiveness at 1 year.

These assessments are summarised in Figure 8.

All families will continue to receive access to the 24/7 helpline during this time. Any participant who reacts at challenge to a previously tolerated level will recommence updosing.

[figure not shown]

Figure 8: Year 3/4 Assessments

Participants who go on to stop all peanut for 12 months (i.e. who pass the 12-week DBPCFC without any loss of tolerance) will be asked to eat 8 roasted peanuts on a monthly basis as a safety measure, to ensure ongoing clinical non-reactivity during this time. Any participant who begins to exhibit symptoms during this 9 month period (prior to final DBPCFC) to the monthly dose of 8 peanuts will be reviewed by the study PI who may take the decision to recommence peanut and not to proceed to the 12 month challenge. This is in order to prevent any participant from reverting back to clinical reactivity that cannot be remedied easily.

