5.8.2 QUALITY OF LIFE ASSESSMENTS

The impact of OIT on participants' quality of life (QoL) will be assessed both from parents' and participants' perspective using abbreviated versions of disease-specific validated "food-allergy quality of life questionnaire" (FAQL-Q) in its parental, ¹⁴ child¹⁵ and teenage¹⁶ forms at baseline, 3, 6, 12, 24 and 36 months in both the active and control groups. These new abbreviated versions have been validated (data submitted for publication). We will also assess the impact of the child's food allergy on parent QoL, using the FAQL-Parent Burden form (which has been validated in a UK population).¹⁷ QoL assessments will be done both prior to and after oral challenges.

The FAQL-questionnaires are based on a 7-point Likert scale and changes greater than 0.5 points over time have been defined as clinically significant. Previous studies have reported a positive effect on QoL following OIT to peanut from the parents' perspective, however, there are no controlled studies which have addressed the impact on QoL as perceived by participants. This is a significant knowledge gap, since there is a concern that while parents report an improved QoL when their child undergoes OIT, the child themselves may experience a worsening of QoL due to frequent side effects and need to alter their activities following OIT doses.

In line with current expert opinion, and to ensure the ability to compare responses consistently during the first 12 months of OIT, children who are age 12 at study commencement will be asked to complete the Teenage versions of the QoL assessments, unless there are difficulties with comprehension which preclude this.

We will also assess parental anxiety before, and 12 and 24 months after their child commencing OIT, using the Perceived Stress Scale.¹⁹

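### The month-12 outcome table in 5.4.1 withdraws OIT failures from the study, against the 24- and 36-month quality-of-life follow-up planned for all children

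*Combined protocol and SAP*

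**What the plan says.** The rule is in the protocol, section 5.4.1, in the outcome column of the Protocol 1 table for the 12-month DBPCFC.

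- For reactions at the lower doses the outcome is "OIT unsuccessful: withdrawn from study". The next row, 1000 mg, has a different outcome: daily peanut continues.
- The footnote makes one exception. A child who reacts at 300 mg but has already tolerated at least one roasted peanut is let through: "then they can continue daily peanut at the previous tolerated dose for a further 12 months, within this protocol".

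Other sections plan later follow-up and do not except these children.

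- Section 5.6, at 24 months: "All subjects will also undergo repeat skin prick testing to commercial crude peanut extract and boiled peanut slurry, and quality-of-life assessments". It also says that children in both groups, "apart from those who passed the tolerance challenge at 13 months, will be offered a further tolerance challenge at 24 months".
- Section 5.7: "All children (in both active and control groups) will be invited to return at the 3 year timepoint".
- Section 3 puts QoL at 6, 12, 24 and 36 months in every subject and their parents. Section 5.8.2 gives the schedule as "at baseline, 3, 6, 12, 24 and 36 months in both the active and control groups".
- Section 4.3, repeated in 7.2: "Subjects who are withdrawn from active treatment will remain in the study for assessment of outcome relating to QoL measures".

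Section 4.3 also lists the circumstances for withdrawal from the study. Failing the month-12 challenge is not one of them.

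**The concern.** Staff cannot apply the 5.4.1 cell as written and also collect 24- and 36-month QoL from everyone. If they follow the cell, the children lost are not a random subset: they are those in whom a full year of OIT failed.

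That matters for the question 5.8.2 sets itself. It is concerned that parents may report better QoL while the child's own QoL worsens, and it wants to learn what failing OIT does to the family. The extra QoL contacts it sets up, at 1 and 6 months, are for children who fail the boiled-peanut check or are withdrawn during active OIT because of a significant reaction. They do not clearly cover a child who completes the year and then fails the month-12 challenge.

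A second, smaller issue is that sustained unresponsiveness at 1 and 3 years is a named secondary outcome (3.1.2), and the plan does not say how children withdrawn under 5.4.1 count in it.

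**Working it through.** This is a check of consistency. The plan's sample size of 46 is not in dispute, and the rule acts only after the month-12 challenge has been recorded.

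**Step 1: whom the rule covers.** Cumulative protein after the 300 mg dose is 3 + 10 + 30 + 100 + 300 = 443 mg. After the 1000 mg dose it is 443 + 1000 = 1443 mg, which is the 1.4 g of the primary endpoint. A child who misses the endpoint at challenge has therefore reacted at 1000 mg or lower. The 1000 mg reactors stay on daily peanut. The separate 1000 mg outcome and the 300 mg footnote place the withdrawal rule at 3 to 300 mg.

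**Step 2: whether the group is foreseeable.** Under 5.3.4.2, a child who cannot tolerate 300 mg at the roasted-peanut challenge stays on 8 boiled peanuts until the 1-year assessment. Such a child has not moved to roasted peanut and would generally not meet the footnote's condition. So the rule can be expected to apply to some children.

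**Step 3: the rule against each other section.**

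| Section | Plan for later follow-up | Against the 5.4.1 cell |
|---|---|---|
| 5.6, skin test and QoL | all subjects, 24 months | direct conflict |
| 3 and 5.8.2, QoL | all subjects and both groups, to 36 months | direct conflict |
| 4.3 and 7.2, retention | off active treatment, stays in for QoL | direct conflict |
| 4.3, withdrawal list | month-12 failure not listed | no support for the cell |
| 5.6, tolerance challenge | all except those who passed at 13 months | soft conflict |
| 5.7, year 3 | all children invited | soft conflict |

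The last two are soft for different reasons. Section 5.6 has the challenge performed as in 5.4, where only children above 1.4 g go on to the off-peanut challenge. Section 5.7 gives its purpose as longer-term tolerance after 2 to 3 years of immunotherapy.

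**Step 4: which analyses are touched.** The primary test (7.2.1) uses the month-12 result. The QoL tests in 7.2.2 are at 6 and 12 months. Both use data due by the month-12 assessment. QoL at 24 and 36 months is collected, but no test of it is listed.

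**Step 5: a ceiling on the number withdrawn.** Inputs from 7.1 are 30 active children, 60% success and 20% loss. Children not reaching 1.4 g: 30 − 0.60 × 30 = 12. Among 0.80 × 30 = 24 assessed: 24 − 0.60 × 24 = 9.6, about 10. These are ceilings, because 1000 mg reactors and footnote cases are not withdrawn. The documents do not give the split, so the range is 0 to 12.

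**Step 6: sustained unresponsiveness.** Section 7.2.2 describes a proportion in the active and control groups, and 7.2 defines arms by allocation. However, 7.2 words intention to treat for the primary analysis only and adds a per-protocol analysis. The denominator at 1 and 3 years is therefore not fixed. The withdrawal rule is only part of the cause: 1000 mg reactors are not withdrawn, yet they also skip the 13-month challenge, so the same question arises for them at 1 year.

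**The case against.** The strongest reply is that the cell means the end of OIT. The neighbouring cells are treatment instructions, and the footnote is about continuing daily peanut. Sections 4.3 and 7.2 would then already keep these children for QoL. The protocol also uses withdrawal loosely: 4.3 lists a serious reaction to OIT as a reason for leaving the study, while 5.8.2 still collects QoL from children withdrawn for a significant reaction. Finally, the table is damaged in the available text, so its row span is inferred, and Figures 7 and 8, which summarise the pathway, are not shown.

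Much of this stands as a view of intent. It does not remove the conflict, because the cell names the study, and the footnote's permission for one subgroup to continue under the protocol suggests that the others do not.

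A reader might go further and infer that later QoL would come only from children helped by OIT. The documents do not support that. Children taken off OIT before month 12 are kept for QoL by 4.3 and 7.2, and controls are in the 24-month QoL under 5.6.

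**Conclusion.** The conflict is real and should be corrected. Read literally, 5.4.1 makes month-12 OIT failures selectively missing from 24- and 36-month QoL and from the 24-month skin test. The primary endpoint, its power, and the listed 6- and 12-month QoL tests are untouched. The harm is to later descriptive QoL, since no test at those times is listed.

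The conclusion rests on the inferred row span (3 to 300 mg) and on taking the cell at its word.

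A reader might infer that the 3-year sustained-unresponsiveness rate will be inflated, by 30/(30 − w) for w children withdrawn. The documents do not support a figure. They do not give w, and they never say that the rate will be taken among children still in the study. Counting withdrawn children as not having sustained unresponsiveness would remove most of any such effect, but it would not recover the missing QoL. The denominator is therefore a secondary clarification.

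**What to change.** 1. In the 5.4.1 table, change the outcome to: OIT ended; remains in follow-up for QoL at 24 and 36 months. Keep the footnote.
2. In 5.6 and 5.7, state that no further challenge is required for these children, and in 5.6 say whether the 24-month skin test still applies to them.
3. As a secondary clarification in 7.2.2, report the 1- and 3-year sustained-unresponsiveness rates over all children randomised to active, counting OIT-unsuccessful children as not having it. Show separately the number missing for other reasons.

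The cost is amendment wording and two questionnaire contacts for a few families who agree to stay. The reported 3-year rate may be lower, and a child who outgrows the allergy after OIT has failed would be counted as not having sustained unresponsiveness. If the authors meant only that OIT ends, the first change simply records it.
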